6.1 Sample size justification and accrual

Recruitment will target enrolling 10 healthy, adult participants without HIV per group for the 2 study groups receiving either 2 doses of INO-6160 followed by 2 doses of INO-6160 alone or in combination with Trimer adjuvanted with 3M-052-AF + Alum (for study schema see [Table 1-1](#)). Up to 5 additional participants, or a total of 25 participants, may be enrolled to ensure sufficient samples for immunogenicity analyses, with a goal of at least 20 contributing to the final analyses. Examples of reasons that might necessitate enrollment of additional participants are provided in Section [1.5](#).

Since enrollment is concurrent with receiving the first vaccination, all participants will provide some safety data. It is possible, however, for immunogenicity data to be missing; previous HVTN and AIDS Vaccine Evaluation Group (AVEG) studies suggest 10% is a reasonable estimate for the rate of missing data. For this reason, the sample size calculations account for 10% of enrolled participants having missing data for the primary immunogenicity endpoints. This 10% missingness accounts for both post-processing variables (eg, problems with samples) and is mitigated by the potential for replacing participants who do not continue with the study.

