6.1.2 Power calculations for safety

The goal of the safety evaluation for this study is to identify safety concerns associated with vaccine administration. The ability of the study to detect SAEs can be expressed by the true event rate above which at least 1 SAE would likely be observed and the true event rate below which no events would likely be observed. The SAEs will be monitored following each dose. For the first 2 doses, study participants in both groups will receive the same sD-NLT-AB05 + IL-12 DNA adjuvant; thus, the safety sample size can be doubled. Specifically, for this two-arm study with sample size $n = 10$ per group ($n = 20^*$ for safety after the first 2 doses), there is at least a 90% chance of observing at least 1 event if the true rate of such an event is 20.6% (10.9%*) or more and there is at least a 90% chance of observing no events if the true rate is 1.05% (0.53%*) or less. Safety data will be evaluated using historical controls. As a reference, in HVTN vaccine trials conducted in the US from April 2008 through March 2018, about 1% of

participants who received placebos experienced an SAE. Binomial probabilities of observing 0 events, 1 or more events, and 2 or more events among 10 (20*) participants receiving study vaccine are presented in [Table 6-3](#) for a range of possible true AE rates. These calculations provide a more complete picture of the sensitivity of this study design to identify potential safety problems with the vaccine.

Table 6-3 Probability of observing 0 events, 1 or more events, and 2 or more events among a group of 10 (20* for the first two doses) study participants for different true event rates.

True event rate (%)	Group size	0 events	1+ events	2+ events
1	10	0.9	0.1	0
4	10	0.66	0.34	0.06
10	10	0.35	0.65	0.26
20	10	0.11	0.89	0.62
30	10	0.03	0.97	0.85
True event rate (%)	Safety size for the first two doses*	0 events	1+ events	2+ events
1	20*	0.82*	0.18*	0.02*
4	20*	0.44*	0.56*	0.19*
10	20*	0.12*	0.88*	0.61*
20	20*	0.01*	0.99*	0.93*
30	20*	0*	1*	0.99*

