6.4.4 Immunogenicity analyses

6.4.4.1 Statistical Analysis to address primary objectives

The first component of the analysis will entail comparing the frequency of HIV-1–specific binding Ab responses 2 weeks following the fourth vaccination. Comparison between the 2 vaccine groups will use Fisher's exact test, while

McNemar's test will be used for paired data (between visits), with a significant difference declared if the 2-sided p-value is ≤ 0.05 .

To compare the magnitude of HIV-1-specific binding Ab responses 2 weeks following the fourth vaccination. Between the 2 vaccine groups, a two-sided Wilcoxon rank sum test with 5% type-I error rate will be performed. Wilcoxon signed rank test with 5% type-I error rate will be performed for paired data.

With the response rates of CD4+ and CD8+ T cell to HIV-1 specific Env peptide pools 2 weeks following the fourth vaccination, the 2 vaccine groups will be compared using Fisher's exact test, and McNemar's test will be used for paired data), with a significant difference declared if the 2-sided p-value is ≤ 0.05 . For each T-cell subset, the positivity call for each peptide pool will include a multiple-comparison adjustment for the number of peptide pools used in the assay using the discrete Bonferroni adjustment. The magnitude of response will be analyzed with two-sided Wilcoxon rank sum test for independent data and Wilcoxon signed rank test for paired data, with 5% type-I error rate. Graphs will be used to display the background-subtracted magnitudes for each participant by protein, treatment arm, and timepoint, with a box plot of data from positive responders superimposed on the individual data values. Statistical testing comparing the magnitudes will be based on positive responders only.

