#### **4 COHORT DEFINITION**

A total of 20 participants were enrolled in the study, 10 in Group 1 and 10 in Group 2.

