### 7.2 General approach

For the statistical analysis of immunogenicity endpoints, data from enrolled participants will be used according to the initial randomization assignment regardless of how many injections they received. Additional analyses may be performed, limited to participants who received all scheduled injections per protocol. Assay results that are unreliable, from specimens collected outside of the visit window, or from HIV-infected participants are excluded. Since the exact date of HIV infection is unknown, any assay data from blood draws 4 weeks, or less, prior to an infected participant's last seronegative sample and thereafter may be excluded. If an HIV-infected participant does not have a seronegative sample post enrollment, then all data from that participant may be excluded from the analysis.

Discrete categorical assay endpoints (eg, response rates) will be analyzed by tabulating the frequency of positive response for each assay by antigen and treatment arm at each timepoint for which an assessment is performed. Crude response rates will be presented with their corresponding 95% CI estimates calculated using the score test method (1). Barnard's tests will be used to compare the response rates between 2 vaccine groups at a given time-point, McNemar's tests will be used for paired data (between visits), with a significant difference declared if the 2-sided p-value is  $\leq 0.05$ .

For quantitative assay data (eg, magnitude of HIV-1 Env-specific binding Ab responses), graphical and tabular summaries of the distributions by antigen, treatment arm, and timepoint will be made. The difference between arms at a specific timepoint will be tested with a nonparametric Wilcoxon rank sum test and the difference between visits will be tested with a nonparametric Wilcoxon signed rank test including all available data regardless of response positivity. Response magnitudes below the limit of detection of the assay will be replaced by half of the limit in the

tests. All statistical tests will be 2-sided and will be considered statistically significant if  $p \leq 0.05$ .

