## 8.6 Binding Antibody Multiplex Assay (BAMA)

The Binding Antibody Multiplex Assay (BAMA) assay will evaluate binding antibody responses of each serum specimen against BG505 SOSIP (vaccine trimer immunogen) and Trimer 4571 (vaccine matched immunogen). The time points to be tested are: Visit 1 (baseline), Visit 5 (Month 1.5, 2 weeks post 2nd vaccination), Visit 7 (Month 3.5, 2 weeks post 3rd vaccination), 9 (Month 6.5, 2 weeks post 4th vaccination), and Visit 10 (Month 12, 6 months post 4th vaccination). Specimens from other time points as well as other HIV antigens and antibody isotypes may be assayed based on the results of the initial assay.

The following readouts, if included in the final Central Assay Plan, will be analyzed for this assay:

- i. Binding Mean Fluorescence Intensity (MFI): The frequency of positive responders (%) will be tabulated to assess HIV binding antibody responses between vaccine groups from MFI readouts. Positivity criteria include (1) the net MFI (MFI – Blank) values are  $\geq$  antigen-specific cutoff at the 1:50 dilution level for IgG (based on the 95th percentile of the baseline visit serum samples and at least 100 MFI minus Blank), (2) the net MFI values are greater than 3 times the baseline (day 0) net MFI, and (3) the MFI values are greater than 3 times the baseline MFI values.
- ii. Titration (EC50/AUC): If high binding magnitude is observed and it is deemed scientifically important by the lab PI, samples may be titrated to calculate antibody titers. The geometric mean titer will be compared between vaccine groups. The overall difference in geometric mean titer between groups at each time point assays will be compared.
- iii. Differential Binding Response: Epitope specificities may be assessed via wildtype-mutant pairs.

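### The between-arm test of BAMA magnitude leaves out the Visit 5 response, a covariate measured before the arms diverge and already planned, and so may give up power in a 20-person trial

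*SAP*

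**What the plan says.** SAP 7.2 sets one rule for quantitative assay data: "The difference between arms at a specific timepoint will be tested with a nonparametric Wilcoxon rank sum test". The test is run "including all available data regardless of response positivity", values below the detection limit are set to half that limit, and significance is two-sided at 0.05. Protocol 6.4.4.1 names the same test for the primary binding-antibody magnitude: "Between the 2 vaccine groups, a two-sided Wilcoxon rank sum test with 5% type-I error rate will be performed". Neither section names a covariate. The between-group comparison of geometric mean titers in SAP 8.6 names none either.

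Treatment is identical at the start. Protocol 6.1.2 says: "For the first 2 doses, study participants in both groups will receive the same sD-NLT-AB05 + IL-12 DNA adjuvant". The schema gives Trimer 4571 only at Months 3 and 6, and only to Group 2. SAP 8.6 lists "Visit 5 (Month 1.5, 2 weeks post 2nd vaccination" among the BAMA time points without any condition.

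On size, SAP section 4 records: "A total of 20 participants were enrolled in the study, 10 in Group 1 and 10 in Group 2". Protocol 6.1 adds that "the sample size calculations account for 10% of enrolled participants having missing data for the primary immunogenicity endpoints".

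**The concern.** The arms differ only in whether the trimer boost is added to a shared DNA prime. The Visit 5 antibody level shows how each person responded to that prime. It is measured after randomization, but it cannot carry an effect of the boost because nobody has yet received it. If people who respond well at Visit 5 also tend to respond well at Visits 7, 9 and 10, part of the spread within each arm is predictable. The unadjusted test treats that part as noise.

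Nothing else in the plan brings Visit 5 into the arm comparison. The signed rank test in SAP 7.2 compares visits, not arms. Protocol 6.4.4.2 permits repeated-measures methods to study change over time, but SAP 7.2 does not keep that option. The covariates in Protocol 6.4.4.3 are predictors of missingness, and SAP 7.3 drops them.

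Protocol 6.1.1 makes the between-group difference in antibody magnitude part of the main analysis goal. With 9 or 10 people per arm, a modest gain in efficiency could decide whether a real difference is detected.

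**Working it through.** **The plan's own figure.** The protocol gives precision for response rates only. It states no power, SD or effect size for magnitude. Table 6-2 uses Agresti-Caffo intervals with n = 9. For 5 against 0 responders:
- p1 = (5+1)/(9+2) = 0.545 and p2 = (0+1)/(9+2) = 0.091, so the difference is 0.455.
- SE = √(0.545×0.455/11 + 0.091×0.909/11) = 0.173.
- The interval is 0.455 ± 1.96×0.173, or 11.5% to 79.4%, as printed.

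All 22 rows reproduce with n = 9. That confirms 9 per arm as the planning basis but says nothing about power for magnitude.

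**Inputs from the documents.** 10 per arm × 0.90 = 9 analysed; two-sided 5% test; all participants included.

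**Assumed inputs.** True difference of 1 or 1.5 SD; normal data; correlation r between Visit 5 and the later visit of 0, 0.3, 0.5 or 0.7, equal in both arms; exact Wilcoxon test.

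**Planned test.** W is the sum of the ranks in one arm. With 9 against 9 the total of all ranks is 18×19/2 = 171. The exact test rejects if W ≤ 62 or W ≥ 171 − 62 = 109. Its attained alpha is 0.040.

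**Adjusted test (Quade).**
1. Rank the later response and the Visit 5 response over all 18 people, using mid-ranks for ties, and centre both sets of ranks at 9.5.
2. Compute the slope b = Σ(RxRy)/Σ(Rx²).
3. Form the residuals z = Ry − bRx.
4. Compare z between arms with an F test on 1 and 16 degrees of freedom.

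**Simulated results, 9 per arm (20,000 or more trials per cell).**

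| | r = 0 | 0.3 | 0.5 | 0.7 |
|---|---|---|---|---|
| Wilcoxon power, 1 SD | 45% | 45% | 45% | 45% |
| Quade power, 1 SD | 47% | 50% | 56% | 70% |
| Quade, 1 SD, 80% of Visit 5 at floor | – | 49% | 52% | 57% |
| Wilcoxon power, 1.5 SD | 79–80% | 79–80% | 79–80% | 79–80% |
| Quade power, 1.5 SD | 80% | 83% | 88% | 95% |
| Quade: SD detectable with 80% power (Wilcoxon 1.50) | 1.50 | 1.44 | 1.33 | 1.13 |

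With no floor, the type I error of the Quade test was 4.9% to 5.2%. With 10 per arm and 1 SD, Wilcoxon power is 51–52%, and Quade power is 53%, 54%, 61% and 75%.

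**Separating test size from the covariate.** At r = 0 the covariate carries no information, yet Quade shows 47% against 45%. Those 2 points reflect the Wilcoxon alpha of 0.040. Net of them, the covariate adds about 50−45−2 = 3, 56−45−2 = 9 and 70−45−2 = 23 points at r = 0.3, 0.5 and 0.7.

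**Cross-check.** In theory the adjusted SD is √(1−r²) of the unadjusted one. The detectable difference should then be about 1.50×0.866 = 1.30 SD at r = 0.5 and 1.50×0.714 = 1.07 SD at r = 0.7. The simulated values of 1.33 and 1.13 are close and slightly larger, as expected for a rank method in a small sample.

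**Unequal correlation.** With 1 SD and r = 0.5 in Group 1 but 0 in Group 2, Quade power is 49%. With 0.7 and 0.2 it is 54–55%.

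**The case against.** The strongest reply is that nothing is wrong with the planned test. An unadjusted rank-sum test in a randomized trial is valid, and preferring a more efficient valid test is an improvement. That stands. A reader might infer that the planned comparison is biased or that its p-values cannot be trusted; the documents support neither.

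The size of the gain is also undocumented. A reader might infer that variation in DNA response is the main removable noise, or that power would rise to 56–70%. The documents give no correlation, SD or effect size, so neither inference is supported. They report no human binding-antibody data after only two DNA doses; the HVTN 098 results in Protocol 2.5 follow the third and fourth. Visit 5 values may therefore cluster at the floor. The adjuvanted protein may also weaken the correlation in Group 2. Both would shrink the gain, though it stayed positive in every case tried. If the true effect is very large (2.5 SD), both tests exceed 99% power and the choice does not matter.

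The scope is narrow. BAMA titration is conditional in SAP 8.6, Visit 5 ICS is contingent in SAP 8.1, and the neutralization plan in SAP 8.2 does not list Visit 5. Protocol 6.4.4.1 also says that magnitude tests use positive responders only, so the figures for 9 per arm apply to the SAP rule and not to that one.

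Finally, enrollment is complete, the SAP is at version 4.0, and SAP 7.4 allows early by-arm analysis. Replacing the main test now could look data-driven. The fix has to allow for that.

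The small-sample objection to models has less force here. Quade uses ranks and a single covariate, and it held its error rate.

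**Conclusion.** The point holds as a matter of efficiency for BAMA net MFI. The arm comparison is unadjusted, Visit 5 precedes any difference in treatment, and the Visit 5 assay is already planned. With 9 per arm and a 1 SD difference, adjustment moves power from 45% to somewhere between 47% and 70% for correlations of 0 to 0.7. About 2 of those points are due to test size. With 80% of Visit 5 values at the floor, the figures are 49% to 57% for correlations of 0.3 to 0.7. Below a correlation of about 0.3 the gain is only a few points, and at 0 there is none from the covariate but also no loss. These figures rest on assumed normal data, effect sizes and correlations. No figure printed in the protocol changes.

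**What to change.** In SAP 7.2, prespecify for BAMA net MFI at Visits 7, 9 and 10 a Quade rank analysis of covariance on all participants. Use Visit 5 net MFI for the same antigen as the single covariate, with mid-ranks for ties and the median rank where Visit 5 is missing. Report the unadjusted Wilcoxon test alongside it.

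- If by-arm BAMA results have already been seen, keep Wilcoxon as the main test and label the Quade analysis supportive.
- Use Visit 5 AUC as the covariate for AUC only if Visit 5 samples are titrated.
- Extend to ICS only if Visit 5 is assayed, and do not extend to neutralization.
- Reconcile the text with Protocol 6.4.4.1, which names Wilcoxon and restricts magnitude tests to positive responders, whereas SAP 7.2 uses everyone.

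The cost is a paragraph of SAP text, the reconciliation with the protocol and a few lines of code. Net MFI needs no new samples or assays. The drawbacks are one added analysis with light assumptions, a rule for a missing covariate, and different tests across assays.

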### 7.3 Missing Data

Based upon previous AIDS Vaccine Evaluation Group and HVTN trials, missing 10% of immunogenicity results for a specific assay is common due to study participants terminating from the study early, problems in shipping specimens, or low cell viability of processed peripheral blood mononuclear cells (PBMCs). Due to the limited sample size of the study, nonparametric tests as mentioned in the previous section will be used assuming the probability of an observation being missing does not depend upon any unobserved covariates and violations of this assumption will have little impact on the estimates and hypothesis tests.

### 7.4 Analyses prior to end of scheduled follow-up visits

Any analyses conducted prior to the end of the scheduled follow-up visits should not compromise the integrity of the trial in terms of participant retention or safety or immunogenicity endpoint assessments. In particular, early analyses by treatment assignment require careful consideration and should be made available on a need-to-know basis only.

A statistical analysis by treatment assignment of a primary immunogenicity endpoint may be performed. The HVTN Laboratory Program will review the analysis report prior to distribution to the protocol chairs, Division of AIDS (DAIDS), vaccine developer, and other key HVTN members and investigators. Distribution of reports will be limited to those with a need to know for the purpose of informing future trial-related decisions. The HVTN leadership must approve any other requests for HVTN immunogenicity analyses prior to the end of the scheduled follow-up visits. Any analyses conducted prior to the end of the study should not compromise the integrity of the trial in terms of participant retention or safety or immunogenicity endpoint assessments.

## 8 IMMUNOGENICITY TABLES AND FIGURES, BY ASSAY

If any participants missed the IM administration at Month 3 in Group 2, the analyses of immunogenicity data collected at Visit 7 (2 weeks after the 3rd vaccination) will be done for all participants, and for the subset of participants who received the full Month 0, Month 1 and Month 3 vaccinations in both study groups. If any participants missed the IM administration at Month 6 in Group 2, the analyses of immunogenicity data collected at Visit 9 (2 weeks after the 3rd vaccination) and Visit 10 (6 months after the 4th vaccination) will be done for all participants, and for the subset of participants who received the full Month 0, Month 1, Month 3 and Month 6 vaccinations in both study groups.

### 8.1 Intracellular Cytokine Staining

Flow cytometry is employed to examine HIV-1-specific CD4+ and CD8+ T-cell responses using a validated ICS assay. The vaccine-matched peptide pools evaluated are:

- BG505 gp120
- BG505 gp41
- A-AB05

Previously cryopreserved specimens are stimulated with the synthetic peptide pools. As a negative control, cells are left unstimulated. As a positive control, cells are stimulated with a polyclonal stimulant, staphylococcal enterotoxin B (SEB). There are no replicates except for the

negative control, which has two replicates. As an additional internal control, cells are stimulated with a CMVpp65 peptide pool.

The total numbers of CD4+ and CD8+ T cells must also exceed certain thresholds. If the number of CD4+ T cells is < 10,000 or the number of CD8+ T cells is < 5,000 for any of the HIV-1 peptide pools or for one of the negative control replicates for a particular sample, data for that stimulation are filtered. If both negative control replicates fail for number of T cells, the sample is retested. If one negative control replicate fails for number of T cells, the negative control replicate with sufficient cells will be used.

To assess positivity for a peptide pool within a T-cell subset, a two-by-two contingency table is constructed comparing the HIV-1 peptide stimulated and negative control data. The four entries in each table are the number of cells positive for IFN- $\gamma$  and/or IL-2 and the number of cells negative for IFN- $\gamma$  and IL-2, for both the stimulated and the negative control data. If both negative control replicates are included, then the sum number of total cells and the sum number of positive cells is used. A one-sided Fisher's exact test is applied to the table, testing whether the number of cytokine-producing cells for the stimulated data is equal to that for the negative control data. Since multiple individual tests (for each peptide pool) are conducted simultaneously, a multiplicity adjustment will be made to the individual peptide pool p-values considered, using the Bonferroni-Holm adjustment method. If the adjusted p-value for a peptide pool is  $\leq 0.00001$ , the response to the peptide pool for the T-cell subset is considered positive. Because the sample sizes (i.e., total cell counts for the T-cell subset) are large, e.g., as high as 100,000 cells, the Fisher's exact test has high power to reject the null hypothesis for very small differences. Therefore, the adjusted p-value significance threshold is chosen stringently ( $\leq 0.00001$ ). If at least one peptide pool for a specific HIV-1 protein is positive, then the overall response to the protein is considered positive. If any peptide pool is positive for a T-cell subset, then the overall response for that T-cell subset is considered positive.

Initially, PBMC samples from the following timepoints will be tested.

- Visit 7 (2 weeks after the 3rd vaccination) (PT Report #1)
- Visit 9 (2 weeks after the 4th vaccination) (PT Report #2)
- Visit 10 (6 months after the 4th vaccination) (PT Report #3)

Visit 5 (2 weeks after the 2nd vaccination) may be assayed contingent on responses from other timepoints and from other immune assays such as BAMA. Additional timepoints may be tested in the future.

### 8.1.1 List of Tables

- Response rate table by lab, T-cell subset, cytokine, peptide pool, visit, day, and treatment arm
- Summary statistics (i.e., min, mean, median, max) among responders for T-cell subset, peptide pool, visit, and treatment arm
- Summary statistics (i.e., min, mean, median, max) among all participants (positive and negative responders) for T-cell subset, peptide pool, visit, and treatment arm
- Response rate and/or response magnitude comparison of treatment arms by T-cell subset, cytokine, and visit.

